5.2.4 Discontinuation of study participation

A participant may be discontinued from protocol participation for the following reasons:

- Participant voluntarily withdraws;
- CRS determines the participant is lost to follow-up;
- The investigational new drug (IND) application sponsor or regulatory authorities stop the study; or,
- PI assessment that it is not in the best interest of the participant to continue participation in the study or that the participant's compliance with the study is not sufficient.

If a participant terminates participation in the study early for any reason, the site PI should consider if the following assessments are appropriate: end-of-study HIV test, complete blood count (CBC with differential, serum chemistry [ALT and creatinine], physical examination, and if indicated, a pregnancy test [see Appendix A and Appendix B]). For participants living with HIV, please see

Section 8.8. If the site PI has questions regarding a termination visit, they should consult with the PSRT.

6 Statistical considerations

This phase-1 study will target recruiting a total of 45 adult participants without HIV aged 18 to 55 years.

In Group 1, a total of approximately 9 participants will receive 3 administrations of sD-NP-GT8 DNA at a dose of 0.4 mg, coformulated with IL-12 DNA at a dose of 0.1 mg at days 1, 29, and 85. Study products will be administered intradermally via EP of the skin on each upper arm.

In Group 2, a total of approximately 18 participants will receive 3 administrations of sD-NP-GT8 DNA at a dose of 1.6 mg, coformulated with IL-12 DNA at a dose of 0.4 mg at days 1, 29, and 85. Study products will be administered intradermally via EP of the skin on each upper arm.

In Group 3, a total of approximately 18 participants will receive 3 administrations of sD-NP-GT8 DNA at a dose of 1.6 mg, coformulated with IL-12 DNA at a dose of 0.4 mg at days 1, 29, and 85. These doses will be administered intradermally via EP of the skin on each upper arm. All participants in Group 3 will also receive 2 administrations of Trimer 4571 at a dose of 100 mcg adjuvanted with 5 mcg of 3M-052-AF + 500 mcg Alum via IM injections into the deltoid muscle at days 85 and 169.

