6.1 Sample size justification and accrual

The protocol team will convene after the final enrolled participant has completed Visit 6 (first FNA visit) to determine if further participants should be enrolled to ensure adequate samples for immunogenicity analysis. Examples of reasons that might necessitate enrollment of additional participants are provided in Section 1.5. If some participants of the original 45 enrolled will not contribute data to some of the immunogenicity analyses, the protocol team may enroll up to 9 additional fully evaluable participants, or a total of 54 participants enrolled, with the goal of 45 contributing to the final immunogenicity analyses. Participants will not be replaced after completion of visit 6, the first FNA visit.

Every study participant will be followed up for an AESI contact at month 18.

Details about the pace of enrollment can be found in Section 1.5.

Since enrollment is concurrent with receiving the first vaccination, all participants will provide some safety data. However, for immunogenicity analyses, data may be missing for a variety of reasons, including participants terminating from the study early, problems in shipping specimens, or high assay background. Immunogenicity data from 17 phase 1, 2, and phase 2a HVTN vaccine trials, which began enrolling after June 2005 (data as of September 2014), indicate that 17% is a reasonable estimate for the rate of missing data. Therefore, the sample-size calculations in Section 6.1.1 below account for about 17% of enrolled participants having missing data.

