6.1.1 Power calculations for immunogenicity

The primary goal of the statistical immunogenicity analyses is to evaluate vaccine-induced immune responses in each treatment group by timepoint. The primary immunogenicity endpoints will be the response rate and magnitude of HIV-1–specific binding Ab responses, as measured by a multiplex assay; the response rate and magnitude of CD4+ and CD8+ T-cell responses to HIV-1– specific Env peptide pools, as measured by flow cytometry; and the frequency of VRC01-class B cells from lymph nodes and periphery following the second and third vaccinations, as measured by B-cell receptor (BCR) sequencing.

The primary and secondary statistical analyses of immunogenicity data will include the following comparisons:

- Group k postbaseline versus Group k at baseline to assess vaccine-induced immune responses within Group k, where k = 1, 2, 3. Groups 2 and 3 may be combined when comparing immune responses measured between baseline and Day 85 and those measured at baseline because participants in these 2 groups will have received the same products until Day 85.
- Group 1 versus Groups 2 and 3 combined to compare immune responses in the low- and high-dose groups (without administration of Trimer 4571) between Day 1 and Day 85.

- Group 1 versus Group 2 to compare immune responses in the low- and high-dose groups (without administration of Trimer 4571) post–Day 85.
- Group 2 versus Group 3 to compare immune responses with and without administration of Trimer 4571 post–Day 85.

[figure not shown]
Response magnitudes may be summarized using sample means and their two-sided 95% confidence intervals (CIs). Response rates will be estimated using empirical proportions; their two-sided 95% CIs will be constructed using the score method described in Agresti and Coull (1998) (53).

Comparisons of response magnitudes between timepoints within individual treatment groups or pooled treatment groups (eg, Groups 2 and 3 postbaseline versus baseline) will be carried out using Wilcoxon signed-rank tests.

Comparisons of response magnitudes between 2 independent groups (eg, Group 2 versus Group 3) within timepoints will be done using Wilcoxon rank-sum tests.

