The power achieved by the Wilcoxon rank-sum and the Wilcoxon signed-rank tests was computed as a function of the effect size for various sample sizes: n = 9, 15, 18, 30, 36, 45, including cases when no data are missing and cases when $\sim 17\%$ of the data are missing. These calculations also describe the power achieved by statistical comparisons of data measured in FNA samples if only 50% of participants enrolled in Groups 2 and 3 (ie, n = 9 participants per group or n = 18 in Groups 2 and 3 combined) consent to providing FNA samples. The calculations assumed that observations are normally distributed and that the number of observations in both groups or timepoints is identical.

The power function of the tests under these scenarios is presented in Figure 6-1. For instance, when comparing 2 independent groups of equal sizes n = 15 (eg. Groups 2 or 3 with about 17% loss to follow-up), the study achieves about 80% power to detect a significant difference at the 5% significance level using a twosided Wilcoxon rank-sum test if the average increase in the standardized (Cohen's) effect size is about 1.1. For example, if the proportion of VRC01-class B cells two weeks after the second vaccination was 1.0% in Group 1 and 2.1% in Group 2, with a standard deviation of about 1.0% in both groups, the standardized effect size would be 1.1 = (2.1%-1.0%)/1.0%, and the study would have approximately 80% to detect a significant difference between the two groups using a two-sided Wilcoxon rank-sum test at the 5% significance level. With a sample size of n = 18 per group (eg, Groups 2 or 3 with no loss to follow-up), the test has about 80% power to detect a significant difference if the standardized effect size is 1.0. Thus, if the proportion of VRC01-class B cells two weeks after the second vaccination was 1.0% in Group 1 and 2.0% in Group 2, with a standard deviation of about 1.0% in both groups, the standardized effect size would be 1.0 = (2.0%-1.0%)/1.0%, and the study would have approximately 80% to detect a significant difference between the two groups using a two-sided Wilcoxon rank-sum test at the 5% significance level.

[figure not shown]

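### The 80% power quoted for Group 1 versus Group 2 needs 15 or 18 people in Group 1, which has 9; at the real sizes it is about 59–63%

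*Protocol*

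**What the plan says.** Protocol Section 6.1.1 gives power for the rank-sum and signed-rank tests at n = 9, 15, 18, 30, 36 and 45, on normal data and on the basis that "the number of observations in both groups or timepoints is identical". It introduces n = 15 and n = 18 as sizes for Groups 2 or 3, with and without losses.

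It then works two examples on the frequency of VRC01-class B cells. The first begins "if the proportion of VRC01-class B cells two weeks after the second vaccination was 1.0% in Group 1 and 2.1% in Group 2", an effect of 1.1 SD at n = 15 per group. The second sets 1.0% in Group 1 against 2.0% in Group 2, an effect of 1.0 SD at n = 18 per group. In each case the conclusion is that "the study would have approximately 80% to detect a significant difference between the two groups" with a "two-sided Wilcoxon rank-sum test at the 5% significance level".

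The sizes are set elsewhere. Section 6 states: "In Group 1, a total of approximately 9 participants will receive 3 administrations". Table 1-1 gives 9, 18 and 18, and Section 6.2 builds Group 1 from 5 lead-in and 4 randomized participants. On missing data, Section 6.1 says that "the sample-size calculations in Section 6.1.1 below account for about 17% of enrolled participants having missing data".

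The list of comparisons in Section 6.1.1 includes, up to Day 85, "Group 1 versus Groups 2 and 3 combined to compare immune responses in the low- and high-dose groups". Group 1 against Group 2 alone is listed only after Day 85. The SAP's sample-size section covers safety only and gives no immunogenicity power.

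**The concern.** The power is computed for two groups of 15 or 18 and then attached to a contrast in which one group has 9. The equal-size assumption is disclosed, but it cannot hold for any between-group comparison that includes Group 1. No unequal-size figure appears in the text. The n = 9 curve describes 9 v 9, not 9 v 18 or 9 v 36. The missing-data allowance turns 18 into 15 and 36 into 30, but the list of sizes has no 7 or 8 for Group 1.

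The example also names the wrong contrast for its time point. Two weeks after the second vaccination is Day 43, where the listed comparison pools Groups 2 and 3.

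Low versus high dose is a listed comparison, and secondary endpoint (a) in Section 3.2 compares antibody responses in Groups 1 and 2 to assess dose sparing. Someone told that this contrast has 80% power could read a non-significant result as support for the low dose, when the risk of missing the stated effect is about twice what the text implies.

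**Working it through.** **Inputs (all from the protocol).** Two-sided Wilcoxon rank-sum test, 5% level, normal data (Section 6.1.1). Group sizes 9, 18, 18 (Table 1-1, Section 6). Missing data 17% (Section 6.1). Standardized effects from the two examples: (2.1 − 1.0)/1.0 = 1.1 and (2.0 − 1.0)/1.0 = 1.0.

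**Sizes after 17% missing.** Group 1: 9 × 0.83 = 7.5, so 7 or 8. Group 2: 18 × 0.83 = 14.9, so 15. Groups 2 and 3 pooled: 36 × 0.83 = 29.9, so 30.

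**Method.** Normal data with SD 1 were simulated 200,000 times per scenario, and the rank-sum test was applied with its exact null distribution. At a power of 60% the simulation standard error is √(0.6 × 0.4/200,000) = 0.0011, or about 0.1 point.

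A hand check uses the normal approximation for a difference in means, power ≈ Φ(δ − 1.96), with δ = d·√(n₁n₂/(n₁ + n₂)). It runs a few points high because it ignores both the small samples and the rank test's loss of efficiency, but it shows the same drop.

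| Comparison | n₁ v n₂ | d | δ | Φ(δ − 1.96) | Exact rank-sum |
|---|---|---|---|---|---|
| Protocol example 1 | 15 v 15 | 1.1 | 1.1 × √7.50 = 3.01 | 85.4% | **79.6%** |
| Protocol example 2 | 18 v 18 | 1.0 | √9.00 = 3.00 | 85.1% | **80.3%** |
| Group 1 v 2, none missing | 9 v 18 | 1.0 | √6.00 = 2.45 | 68.8% | **61.6%** |
| Group 1 v 2, 17% missing | 7 v 15 | 1.1 | 1.1 × √4.77 = 2.40 | 67.1% | **58.8%** |
| Group 1 v 2, 17% missing | 8 v 15 | 1.1 | 1.1 × √5.22 = 2.51 | 71.0% | **63.4%** |
| Group 1 v 2+3, none missing | 9 v 36 | 1.0 | √7.20 = 2.68 | 76.5% | **71.0%** |
| Group 1 v 2+3, 17% missing | 7 v 30 | 1.1 | 1.1 × √5.68 = 2.62 | 74.6% | **68.5%** |
| Group 1 v 2+3, 17% missing | 8 v 30 | 1.1 | 1.1 × √6.32 = 2.76 | 78.9% | **73.6%** |

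The first two rows reproduce the protocol's 80%, so the method agrees and only the size of Group 1 differs. A comparison of 9 v 18 carries the information of 2 × 9 × 18/27 = 12 per group, not 18.

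**Cross-check.** A plain noncentral-t calculation gives 65.3% for 9 v 18 at d = 1.0 and 62.8% for 7 v 15 at d = 1.1. Scaling the sample sizes by 3/π for the rank test gives 63.2% and 60.6%.

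**Effect needed for 80% power (exact test).** Against Group 2: 1.24 (9 v 18), and 1.34 to 1.42 (8 or 7 v 15). Against Groups 2 and 3 pooled: 1.11 (9 v 36), and 1.20 to 1.26 (8 or 7 v 30). With an SD of 1.0% these are also differences in percentage points.

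**The case against.** The strongest reply is that this is a labelling slip. The equal-size figures are right, the text ties 15 and 18 to Groups 2 or 3, and only the group names in two illustrations are wrong. That is a fair account of the cause. It does not rescue the sentences, which state a power for this study and a named contrast, and which are the only place where power is translated into an endpoint.

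Second, at Day 43 the relevant contrast is the pooled one, where the shortfall is smaller. This stands in part. With 9 v 36 at d = 1.1 and no missing data, power is 79.0%. But the protocol pairs d = 1.1 with 17% missing and d = 1.0 with none, and on those pairings the pooled contrast has 68.5% to 73.6% and 71.0%.

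Third, up to 9 extra participants may be enrolled, so Group 1 might keep 9 evaluable. That is possible, though optional and closed after Visit 6. At d = 1.1 it gives 67.0% (9 v 15) or 69.8% (9 v 18), still short.

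Fourth, comparing Group 1 with its own baseline is properly covered by the n = 9 signed-rank curve when no data are missing. That is correct; the point concerns between-group comparisons only.

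Fifth, the plan says comparisons between groups are to be read with caution and plans no equivalence conclusion. This tempers the consequence, but a reader judges a non-significant result partly by the power stated for it.

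**Conclusion.** The concern holds. For the contrast that the protocol names, power at its own assumed effects is 61.6% with no missing data and 58.8% to 63.4% with 17% missing, against a stated 80%. For the pooled contrast that applies before Day 85 it is 71.0%, and 68.5% to 73.6%, respectively. The risk of missing the stated Group 1 v Group 2 effect is therefore 37% to 41%, not 20%.

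These figures rest on the protocol's own assumptions: normal data, a common SD, the exact two-sided 5% rank-sum test, and the two effect sizes in its examples. Figure 6-1 was not available to check, but by its description it shows equal sizes and so cannot supply these values. The general 80% statements remain correct for Group 2 versus Group 3.

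**What to change.** In Section 6.1.1:

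- Rename the groups in both worked examples to Group 2 versus Group 3, and move them to a time point after Day 85, where that comparison is planned.
- Add power for Group 1 v Group 2 at 9 v 18 and 7–8 v 15, and for Group 1 v Groups 2 and 3 pooled at 9 v 36 and 7–8 v 30, with the effect detectable at 80% power for each.
- If an example two weeks after the second vaccination is kept, use the pooled comparison.
- State which contrast governs secondary endpoint (a) after the first two vaccinations, since Section 3.2 names Group 1 v Group 2 and Section 6.1.1 pools.

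The cost is a few sentences and one recomputed figure, and the stated power becomes less favourable. The calculation gives no reason to enrol more participants or to alter the tests.

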6.1.2 Power calculations for safety

The goal of the safety evaluation for this study is to identify safety concerns associated with vaccine administration. The ability of the study to detect SAEs (see Section 9.2) can be expressed by the true event rate above which at least 1 SAE would likely be observed and the true event rate below which no events would likely be observed. Specifically, for each treatment group of size n = 18 (Groups 2 or 3), there is at least a 90% chance of observing at least 1 event if the true rate of such an event is 12.5% or more, and there is at least a 90% chance of observing no events if the true rate is 0.53% or less. When pooling Groups 2 and 3 together (n = 36), there is at least a 90% chance of observing at least 1 event if the true rate of such an event is 6.5% or more, and there is at least a 90% chance of observing no events if the true rate is 0.29% or less. Safety data will be summarized as described in Section 6.4.3 and evaluated using historical controls. As a reference, in HVTN vaccine trials conducted in the US from April 2008 through March 2018, about 1% of participants who received placebos experienced an SAE.

Binomial probabilities of observing 0 events, 1 or more events, and 2 or more events among 9 (or 18 or 36 or 45) participants receiving the study vaccine are presented in Table 6-1 for a range of possible true AE rates. These calculations provide a more complete picture of the sensitivity of this study design to identify potential safety problems with the vaccine.

Table 6-1 Probability of observing 0 events, 1 or more events, and 2 or more events among a group of 9, 18, 36, or 45 study participants for different true event rates

True event rate (%)	Arm size	0 events	1+ events	2+ events
1	9	0.91	0.09	0.00
4	9	0.69	0.31	0.05
10	9	0.39	0.61	0.23
20	9	0.13	0.87	0.56
30	9	0.04	0.96	0.80
1	18	0.83	0.17	0.01
4	18	0.48	0.52	0.16
10	18	0.15	0.85	0.55
20	18	0.02	0.98	0.90
30	18	0.00	1.00	0.99
1	36	0.70	0.30	0.05
4	36	0.23	0.77	0.42
10	36	0.02	0.98	0.89
20	36	0.00	1.00	1.00
30	36	0.00	1.00	1.00
1	45	0.64	0.36	0.07
4	45	0.16	0.84	0.54
10	45	0.01	0.99	0.95
20	45	0.00	1.00	1.00
30	45	0.00	1.00	1.00

An alternative way of describing the statistical properties of the study design is in terms of the 95% CI for the true rate of an AE based on the observed data. Table 6-2 shows the two-sided 95% CIs for the probability of an event based on a particular observed rate. Calculations are done using the score test method for CIs described in Agresti and Coull formula 2 (53). If none of the 18 participants receiving the study vaccine in Groups 2 or 3 experience a safety event, the 95% two-sided upper confidence bound for the true rate of such events in the total vaccinated population is 17.6%. Table 6-2 also includes CIs for groups of size n = 9 (Group 1 alone), n = 36 (Groups 2 and 3 pooled together), and n = 45 (all 3 treatment groups combined).

Table 6-2 Two-sided 95% Cls for the probability of observing a safety event based on observing a particular rate of safety endpoints in a group of 18, 36, or 54 study participants

Observed event rate	95% CI (%)	
0/9	[0;29.9]	
1/9	[2.0; 43.5]	
2/9	[6.3;54.7]	
0/18	[0; 17.6]	
1/18	[1.0; 25.8]	
2/18	[3.1; 32.8]	
0/36	[0; 9.6]	
1/36	[0.5; 14.2]	
2/36	[1.5; 18.1]	
0/45	[0; 6.6]	
1/45	[0.3; 9.8]	
2/45	[1.0; 12.5]	

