*Up to 9 additional participants may be enrolled (for a total of up to 54), if needed, to have approximately 45 participants contribute to immunogenicity analyses. Specific scenarios that could necessitate enrollment of additional participants in order to prevent loss of statistical power of the study include, but are not limited to, the following: loss of participants due to moving, withdrawal of consent, missing vaccine visits, inability to complete FNA, or variations in the clinical care due to unpredictable events. Participants will not be replaced after completion of visit 6, the first FNA visit.

** Initial enrollment will be restricted to 1 participant per day for the first 5 participants in Group 1, and enrollment will pause after the first 5 participants are enrolled in Group 1. The Protocol Safety Review Team (PSRT) will review cumulative safety information for these first 5 participants recorded through the visit scheduled 2 weeks post–first vaccination and will determine whether it is safe to proceed with full enrollment in all groups.

[†]For the first five participants in Group 3, the Month 3 vaccination will be limited to 1 participant per day.

§FNA will not be conducted for Group 1 but may be optional for Groups 2 and 3 and will be offered to participants during screening. A minimum target of 9 participants in these groups will be asked to provide consent for receiving the FNA.

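### The three 45-participant rows of the safety confidence-interval table (Protocol Table 6-2, SAP Table 8-2) were computed with n = 54, so their upper bounds are too low

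*Protocol*

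**What the plan says.** Protocol Section 6.1.2 introduces the table as follows: "Table 6-2 shows the two-sided 95% CIs for the probability of an event based on a particular observed rate". It names the score test method as the basis of the calculation. It adds that the table covers Group 1 alone (n = 9), Groups 2 and 3 pooled (n = 36), and "n = 45 (all 3 treatment groups combined").

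The last three rows are labelled 0/45, 1/45 and 2/45, with intervals [0; 6.6], [0.3; 9.8] and [1.0; 12.5].

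The title of the same table describes intervals "based on observing a particular rate of safety endpoints in a group of 18, 36, or 54 study participants". It names 54, which no row label uses, and omits 9 and 45, which row labels do use.

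On sample size, the opening of Protocol Section 6 states: "This phase-1 study will target recruiting a total of 45 adult participants without HIV aged 18 to 55 years". The number 54 appears elsewhere only as a ceiling, in the notes to the schema in Section 1.5: "Up to 9 additional participants may be enrolled (for a total of up to 54), if needed". Section 6.1 repeats that ceiling.

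SAP Section 8 carries the same explanatory text, and SAP Table 8-2 has the same title and the same twelve intervals.

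**The concern.** The title says 54, while the text and the row labels say 45. One of them must be wrong, and the question is which number was used in the calculation. If it was 54, the intervals for the whole study are narrower than 45 participants can support.

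The 0/45 row has the tightest zero-event bound in the table. It answers the question a safety reader asks of a first-in-human study: if nothing is seen in anyone, how high could the true rate still be? An upper bound that is too low overstates the reassurance. Because the SAP governs the Safety Monitoring Board reports and the final safety report, the figure can also be carried into later documents.

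**Working it through.** **Inputs.** Two-sided 95% level and score method (Protocol Section 6.1.2); x = 0, 1, 2 events; n = 9, 18, 36 and 45 (row labels and text), and n = 54 (table title).

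**Formula.** With z = 1.96 (z² = 3.8415), the score limits are

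(x + z²/2 ± z·√[x(n − x)/n + z²/4]) / (n + z²).

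For x = 0 the lower limit is 0 and the upper limit reduces to z²/(n + z²).

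**Step 1: reproduce the rows not in dispute.** For 0/18, 3.8415/21.8415 = 17.59%, which is the 17.6% printed in the text and the table. All nine rows agree with the print:

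| Row | Recomputed (%) | Printed (%) |
|---|---|---|
| 0/9 | 0 to 29.91 | [0; 29.9] |
| 1/9 | 1.99 to 43.50 | [2.0; 43.5] |
| 2/9 | 6.32 to 54.74 | [6.3; 54.7] |
| 0/18 | 0 to 17.59 | [0; 17.6] |
| 1/18 | 0.99 to 25.76 | [1.0; 25.8] |
| 2/18 | 3.10 to 32.80 | [3.1; 32.8] |
| 0/36 | 0 to 9.64 | [0; 9.6] |
| 1/36 | 0.49 to 14.17 | [0.5; 14.2] |
| 2/36 | 1.54 to 18.14 | [1.5; 18.1] |

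The method is therefore confirmed.

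**Step 2: the rows labelled /45.** Zero events:

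- n = 45: 3.8415/48.8415 = 7.87%
- n = 54: 3.8415/57.8415 = 6.64%

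One event, n = 45: (1 + 1.9207 ± 1.96·√[44/45 + 0.9604]) / 48.8415 = (2.9207 ± 2.7286)/48.8415, which is 0.39% to 11.57%.

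| Events | Printed as /45 | Score, n = 45 | Score, n = 54 | Upper bound too low by |
|---|---|---|---|---|
| 0 | [0; 6.6] | 0 to 7.87 | 0 to 6.64 | 7.87 − 6.64 = 1.23 points |
| 1 | [0.3; 9.8] | 0.39 to 11.57 | 0.33 to 9.77 | 11.57 − 9.77 = 1.80 points |
| 2 | [1.0; 12.5] | 1.23 to 14.83 | 1.02 to 12.54 | 14.83 − 12.54 = 2.29 points |

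In relative terms: 1.23/7.87 = 15.6%, 1.80/11.57 = 15.6%, 2.29/14.83 = 15.4%.

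**Step 3: rule out other explanations.**

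- *Another n.* Scanning n = 45 to 59, only n = 54 reproduces all six printed limits. The neighbours already fail: n = 53 gives upper bounds 6.8, 9.9, 12.8, and n = 55 gives 6.5, 9.6, 12.3.
- *Another method at n = 45.* The upper bound for 0/45 would be 7.87 (Clopper-Pearson), 9.38 (Agresti-Coull adjusted Wald), 9.80 (score with continuity correction), 5.40 (Jeffreys) or 5.67 (90% score). None is 6.6.

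**Step 4: does the error extend to Table 6-1?** No. At a true rate of 1%, the printed probability of no events among 45 is 0.64. The calculation gives 0.99^45 = 0.64, whereas 0.99^54 = 0.58. The two adjacent tables therefore use different sample sizes under the same label.

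**The case against.** **The table is a planning illustration.** No pause rule, enrollment step, sample size or analysis depends on these rows. The pause rules respond to individual events, the first safety review is a judgement on five participants, and the planned safety analyses are counts and percentages. Intervals in a final report would come from observed data. This stands, and it limits the practical consequence.

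**The difference hardly changes interpretation.** Against the placebo SAE rate of about 1% cited in Section 6.1.2, a zero-event bound of 6.6% and one of 7.9% both leave rare events unexcluded. The pool also mixes three regimens, and the one bound discussed in the prose (0/18, 17.6%) is correct. This too is fair.

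**Perhaps 54 was intended.** The title and the computed values agree on 54, enrollment may reach 54, and all enrolled participants contribute safety data. At full expansion the printed intervals would be right for 0/54, 1/54 and 2/54. This carries less weight. The row labels, the accompanying sentence, the recruitment target and the 45-participant rows of Table 6-1 all point to 45, and 54 is reached only if all nine optional participants are added. Even on this reading the rows are mislabelled, so the table still needs correcting.

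**Conclusion.** The error is confirmed. The three intervals labelled /45 are the n = 54 score intervals. For 45 participants the correct values are [0; 7.9], [0.4; 11.6] and [1.2; 14.8]. The lower limits for one and two events are also slightly low (0.3 against 0.4, and 1.0 against 1.2).

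The conclusion rests on the score method named in the documents, which the nine other rows confirm, and on reading the rows as their labels and the text describe them. That 54 was taken from the enrollment ceiling is a plausible inference which the documents do not state; the mismatch does not depend on it.

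The numbers should not remain as printed: the error is certain, it overstates safety precision, and it appears in both documents. Its practical weight is modest because nothing in the trial's conduct turns on these rows.

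**What to change.** In Protocol Table 6-2 and SAP Table 8-2:

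- Replace the three rows with 0/45 [0; 7.9], 1/45 [0.4; 11.6] and 2/45 [1.2; 14.8].
- Change the group sizes in the title to 9, 18, 36, or 45.
- If the expansion case is wanted, keep the existing intervals as additional rows labelled 0/54, 1/54 and 2/54, and add 54 to the title and the text.

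The cost is five changed limits and one title in each document (the lower limit for 0/45 stays at 0), and the stated bounds become slightly less favourable. Design, sample size and analyses are unaffected. SAP Section 1 already provides for a review and update before the first Safety Monitoring Board report and again before the final analysis, which gives a natural occasion for the SAP correction.
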